APPENDIX 1: sub-studies

This appendix elaborates on the study methods of the sub-studies of the Simple Intensive Care Studies-I (SICS-I). Per sub-study, we elaborate on the research question, variable of interest, timing of the measurement in the basic study, additional exclusion criteria, sample size calculations, and the analyses. on the sub-study procedure, additional exclusion criteria, and primary and secondary outcomes.

The conclusions based on the analyses in the sub-studies are explorative in nature and must all be confirmed in separate (external) validation cohorts.

1. Near infra-red spectroscopy

1.1. Research question

Which clinical examination, biochemical, and haemodynamic variables are associated with tissue (muscle) oxygen saturation (StO₂) measured by near-infrared spectroscopy (NIRS)?

1.2. Variable of interest

StO₂ was measured by NIRS with the Inspectra StO₂ tissue oxygenation monitor, model 650 (Hutchinson Technology, Inc., Hutchinson, Minnesota, USA). We used a 15-mm probe to measure the StO₂ at a depth of 14mm at two sites: the thenar eminence and the distal end of the vastus medialis muscle. The average StO₂ value was calculated over 30 seconds after one minute of signal stabilisation.

1.3. Timing of measurement

During inclusion in the basic study (one-time snapshot).

1.4. Additional exclusion criteria

Liver failure (increased bilirubin levels cause interferences with StO₂ measurements), patients with dark skin complexion (large quantities of melanin interfere with the near-infrared light emanated by the probe).

1.5. Sample size, power and detectable difference

We will conduct analysis of this sub-study with 32 patients, in which we will regress their values of NIRS against clinical examination findings such as central-to-toe temperature difference. Prior data indicate that the standard deviation of central-to-toe temperature is 4.1 with and estimated standard deviation of the regression errors of 23. If the true slope of the line obtained by regressing NIRS against central-to-toe temperature is 3.406, we will be able to reject the null hypothesis that this slope equals

zero with probability (power) 80%. The type I error probability associated with this test of this null hypothesis is 0.015.

1.6. Runtime

1 April 2015 until 5 August 2015.

1.7. Primary analysis

The association between clinical, biochemical and haemodynamic variables and tissue (muscle) StO₂ measured by NIRS at the knee.

1.8. Secondary analyses

The association between clinical, biochemical and haemodynamic variables and tissue (muscle) StO₂ measured at the thenar muscle.

The association between tissue (muscle) StO₂ measured by NIRS and 90-day mortality.

2. Pulmonary ultrasound

2.1. Research question

What is the diagnostic accuracy of pulmonary oedema measured with pulmonary ultrasonography and auscultation for pulmonary crackles compared to pulmonary oedema diagnosed on a chest radiograph?

2.2. Variables of interest

Pulmonary ultrasound was conducted with the cardiac probe M3S of M4S with default cardiac imaging and maximal frequency (3.6 MHz) setting of the General Electric Vivid-S6 mobile ultrasound machine. We measured the presence or absence of B-lines at the six locations specified in the BLUE-protocol. The presence of a B-profile was defined by three or more B lines observed in at least three of the six BLUE points, or in two of the four lower BLUE points.

Pulmonary oedema was diagnosed by the radiologist who reviewed chest radiographs as part of daily care. The radiologist was blinded for the variables collected in our study.

2.3. Timing of measurement

During inclusion in the basic study (one-time snapshot).

2.4. Additional exclusion criteria

Patients after pulmonary transplantation.

2.5. Sample size, power and detectable difference

Due to a set sample size we were able to estimate the precision of our estimate (i.e. the maximum marginal error). We calculated the maximum marginal error with the formulas of Hajian-Tilaki (49) and information from Simel et al. (50) and Flauhault et al (51). In our pilot data, the prevalence of pulmonary oedema diagnosed by chest radiography was 18.6%, and a B-profile measured with pulmonary ultrasonography had a sensitivity of 54.5% and a specificity of 93.8%. Based on 446 validated chest radiography images, a type-I error of 0.015 (with a corresponding Z-value of 2.17), and the abovementioned prevalence, sensitivity and specificity, the estimated maximal marginal error for sensitivity is 11.9% and 2.7% for specificity.

2.6. Runtime

Since 1 September 2015.

2.7. Primary analysis

The diagnostic test accuracy of a B-profile measured with pulmonary ultrasonography compared to pulmonary oedema diagnosed by chest radiography.

The diagnostic test accuracy of pulmonary crackles assessed with auscultation compared to pulmonary oedema diagnosed by chest radiography.

2.8. Secondary analysis

The statistically and clinically significant difference in CO between patients with and without a B-profile.

3. Positive end-expiratory pressure challenge

3.1. Research question

Is an increase in positive end-expiratory pressure (PEEP) associated with a decrease in cardiac output?

3.2. Variable of interest

During the PEEP-challenge, an additional 10 cm H₂O of PEEP was temporarily applied when supervised by the treating ICU physician. The PEEP was elevated for a maximum duration of 5 minutes during which the changes in cardiac output, heart rate, blood pressures and central venous pressure were recorded.

3.3. Timing of measurement

During inclusion in the basic study and after temporary PEEP application (repeated measurements).

3.4. Additional exclusion criteria

The attending ICU physician was not interested in fluid responsiveness at time of inclusion.

3.5. Sample size, power and detectable difference

We are planning a study with paired measurements in 25 patients. Prior pilot data indicate that the difference in the cardiac output of matched pairs is normally distributed with standard deviation 0.60. If the true difference in the cardiac output before and after application of PEEP is 0.42, we will be able to reject the null hypothesis that this response difference is zero with probability (power) 80%. The type I error probability associated with this test of this null hypothesis is 0.015.

3.6. Runtime

1 September 2015 until 3 January 2016.

3.7. Primary analysis

The association between PEEP increase and cardiac output.

3.8. Secondary analysis

None.

4. Right ventricular function and mortality

4.1. Research question

Is right ventricular (RV)-function measured by the tricuspid annular plane systolic excursion (TAPSE) and peak tissue Doppler systolic velocity in the tricuspid annulus (RV s') independently associated with 90-day mortality?

4.2. Measurement method

TAPSE and RV s' have been measured with the cardiac probe M3S of M4S with default cardiac imaging setting of the General Electric Vivid-S6 mobile ultrasound machine. Both measurements were obtained in the AP4CH view. TAPSE was assessed in M-mode, after placing the cursor on the junction of the tricuspid valve and the RV free wall. RV s' was assessed in the tissue velocity imaging mode highlighting the area of interest. The pulsed Doppler sample volume was placed at the tricuspid level of the RV free (i.e. lateral) wall and the longitudinal velocity of excursion was measured.

4.3. Timing of measurement

During inclusion in the basic study (one-time snapshot).

4.4. Additional exclusion criteria

None.

4.5. Sample size, power and detectable difference

In our design paper, we have 112 patients with an impaired TAPSE and 279 patients with a normal TAPSE (controls). Pilot data indicate that the 90-day mortality proportion among controls is 0.28⁷. We will be able to detect true relative risks of 0.46 or 1.62 in patients with impaired TAPSE relative to controls with probability (power) 80%. The type I error probability associated with this test of the null hypothesis that this relative risk equals 1 is 0.015. We will use an uncorrected chi-squared statistic to evaluate this null hypothesis.

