Analysis of mortality will be performed using time-to-event data (patients were censored at 90-days of follow-up). Categorical variables will be analysed using the log-rank test and continuous variables will be assessed using a univariable Cox proportional hazard regression analysis. Analysis of mortality proportion will be presented by Kaplan-Meier survival curves when independent variables are dichotomous or categorical. A univariable Cox regression analysis will be conducted on 22 clinical examination, haemodynamic and biochemical variables with 90-day mortality as the dependent variable. Covariates with a $p < 0.25$ in the univariable analysis will be included in the multivariable model. We will include the SAPS-II score in our multivariable Cox regression model of 90-day mortality. The SAPS-II is a predictive score for in-hospital mortality and includes seventeen covariates among which age, haemodynamic and biochemical variables, and presence of metastatic or haematological cancer (21). The proportionality assumption will be tested by using the Schoenfeld and scaled Schoenfeld residuals. We will test the proportionality of the model as a whole and the proportionality for each predictor and reject proportionality in case of significant test findings ($p < 0.05$). We will plot graphs of the scaled Schoenfeld assumption, where horizontal lines in the graph indicate that the proportionality assumption is not violated. We will also construct log-log plots, where two parallel lines indicate that proportionality was not violated. The goodness of fit of the final model will be evaluated

by using the Cox-Snell residuals. In our Cox regression models, at least 15 events are necessary for each variable included in the final model (22,23).

6.2.4. *Validation (both)*

Because of the fixed sample size of our study, we will use bootstrapping validation to assess the accuracy of our model. We will randomly select 1075 individuals from the dataset with replacement, build our model on the bootstrapped sample and validate it on the original data. We will repeat this process 100 times and include a variable into our final model if it was significant in at least 80 models. We will still emphasise the hypothesis-generating aspect of our findings. We aim to validate our findings in an independent cohort in the future.

6.3. **Sensitivity and subgroup analyses**

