4.7. Primary analysis

The association between RV-function measured by TAPSE or RV s' and 90-day mortality.

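### Sub-study 4 asks whether RV function is independently associated with 90-day mortality, but the only test and power figure stated are for an unadjusted two-group comparison of TAPSE

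*SAP*

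**What the plan says.** All sub-study references are to the SAP, Appendix 1, sub-study 4.

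- Section 4.1 asks whether TAPSE and RV s' are "independently associated with 90-day mortality".
- Section 4.2 describes TAPSE as an M-mode measurement and RV s' as a tissue Doppler velocity. Both are continuous measurements.
- Section 4.5 reports from the design paper that "we have 112 patients with an impaired TAPSE and 279 patients with a normal TAPSE (controls"), takes control 90-day mortality as 0.28, and gives as detectable "true relative risks of 0.46 or 1.62 in patients with impaired TAPSE relative to controls with probability (power) 80" per cent. It adds "The type I error probability associated with this test of the null hypothesis that this relative risk equals 1 is 0.015" and closes with "We will use an uncorrected chi-squared statistic to evaluate this null hypothesis".
- Section 4.7 gives the primary analysis as "The association between RV-function measured by TAPSE or RV s' and 90-day mortality". It names no model, covariate or cut-off.

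No part of sub-study 4 gives the value that separates impaired from normal TAPSE, and RV s' has no power statement.

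The main SAP handles mortality differently. Sections 6.1.2 and 6.2.3 treat it as time-to-event data. Under 6.2.3 categorical predictors get a log-rank test, "continuous variables will be assessed using a univariable Cox proportional hazard regression analysis", and SAPS-II enters the multivariable Cox model. Section 5.4.2 censors patients lost to follow-up. Sections 2.2.3 and 7 say that this SAP covers the basic study and that SAPs for the sub-studies will follow.

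**The concern.** The stated test does not match the stated question. Independent association means an association that remains after other predictors of death are accounted for. A 2 x 2 chi-squared test contains no other predictors, so a positive result could reflect general severity of illness. The test also ignores when deaths occurred and cannot handle a censored patient, although the main SAP provides for both.

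The 80% power belongs to the unadjusted comparison. A reader of 4.1 and 4.5 together would take it as power for the adjusted question.

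The cut raises two further issues. With no threshold written down, the split could be chosen after the data are seen, which section 7 says the SAP was drafted to avoid. Splitting a continuous measurement can also discard information; how much depends on the shape of the relation with mortality.

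**Working it through.** **Inputs from Appendix 1, section 4.5.** 112 impaired and 279 normal patients (391 in total, impaired share 112/391 = 0.286); control mortality 0.28; alpha 0.015, taken as two-sided (z = 2.432); relative risk 1.62 or 0.46.

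**1. The plan's own figure.** Chi-squared test without continuity correction, pooled variance under the null:

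power = Φ[(|p1 − p0| − 2.432 × SE0) / SE1]

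- RR 1.62: p1 = 0.28 × 1.62 = 0.4536. Pooled risk = (279 × 0.28 + 112 × 0.4536)/391 = 0.330. SE0 = 0.0526, SE1 = 0.0542. Power = Φ[(0.1736 − 0.1279)/0.0542] = Φ(0.843) = 0.800.
- RR 0.46: p1 = 0.1288. Pooled risk = 0.237. SE0 = 0.0475, SE1 = 0.0415. Power = Φ[(0.1512 − 0.1157)/0.0415] = Φ(0.856) = 0.804.

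Solving for exactly 80% gives 1.620 and 0.462. The stated figures are correct for the two-sided, unadjusted comparison.

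**2. The same comparison after adjustment.** Let R² be the squared multiple correlation between impaired TAPSE and the covariates. The documents give no value, so a range is assumed. Counting variance inflation only:

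power = Φ[(2.432 + 0.842) × √(1 − R²) − 2.432]

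| Assumed R² | Power at RR 1.62 |
|---|---|
| 0 | 0.80 |
| 0.05 | 0.78 |
| 0.10 | 0.75 |
| 0.20 | 0.69 |
| 0.30 | 0.62 |

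**3. Cut versus continuous TAPSE, both unadjusted.** The documents give neither the distribution of TAPSE nor the shape of its relation with mortality, so both are assumed. For a normal TAPSE cut at the 28.6th percentile with a smooth effect, the cut keeps φ(z)²/[q(1 − q)] = 0.567 of the information, where q = 112/391 and z is its normal quantile. Continuous power is then Φ(3.274/√0.567 − 2.432) = 0.97.

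Simulations of 391 patients (10,000 to 20,000 runs per case), with group risks held at 0.454 and 0.28 and a straight-line term for continuous TAPSE, gave:

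| Assumed truth | Continuous | Cut | Difference (points) |
|---|---|---|---|
| Linear logit, normal TAPSE | 0.96 | 0.79 to 0.80 | +16 to +17 |
| Linear logit, other distributions | 0.95 to 0.99 | 0.79 to 0.80 | +16 to +19 |
| Risk flat above the cut, or from 0.5 SD above it | 0.61 to 0.86 | 0.79 to 0.81 | −20 to +6 |
| Pure step at the cut | 0.53 | 0.80 | −27 |

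**4. Room for an adjusted model.** If both groups had 0.28 mortality, there would be about 391 × 0.28 = 109 deaths. At the 15 events per variable required in section 6.2.3, that allows 109/15 ≈ 7 terms. RV function, one non-linear term and SAPS-II need three.

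**The case against.** A reader might infer that sub-study 4 will be analysed by the chi-squared test alone. The document does not establish that. The sentence closes a section on sample size and power. The identical sentence closes the basic study's power section (3.2.2), yet that study is analysed by Cox regression with SAPS-II (6.2.3). Sections 2.2.3 and 7 defer the sub-study SAPs, and the appendix calls the sub-study conclusions exploratory. The word independently stands in 4.1 but not in the Table 1 version of the question or in 4.7. The 391 patients are a design-paper count and recruitment to the sub-study was open-ended, so the final number may differ.

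A reader might also infer that the cut simply costs 17 points of power. The documents do not support that either. The figure needs a roughly normal TAPSE and a smooth effect, and other shapes remove or reverse it. The 80% in 4.5 is already the power of the cut comparison, so it is not overstated as such.

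These objections settle what may be claimed, but they do not remove the mismatch. The opening of Appendix 1 says it elaborates on the analyses of each sub-study. For the basic study, 6.2.3 states the real model beside the power sentence; sub-study 4 has no such counterpart. If the chi-squared sentence is only a power approximation, the text should say so.

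**Conclusion.** The point holds as a mismatch between question, test and power statement. Appendix 1 section 4.1 asks for independent association. Section 4.5 gives a test and a power figure for an unadjusted two-group comparison, and 4.7 supplies no model. This conclusion needs no numerical assumption.

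The relative risks of 1.62 and 0.46 are arithmetically right for that comparison, but the 80% does not carry over to the adjusted question. The fall to 0.75, 0.69 or 0.62 rests on assumed R-squared values and counts variance inflation only.

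The gain from keeping TAPSE continuous is conditional: about 16 to 17 points, unadjusted, if TAPSE is roughly normal and risk changes smoothly; none or negative if risk is a threshold at the cut. It has not been computed for the adjusted Cox model recommended here. The change should be made, since it settles what the sub-study can claim at little cost.

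**What to change.** Amend Appendix 1, sections 4.5 and 4.7, and carry the same text into the sub-study SAP:

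1. State the primary analysis as a Cox model of 90-day mortality with TAPSE, and separately RV s', as a continuous variable adjusted for SAPS-II, in line with 6.2.3. Report hazard ratios with 98.5% confidence intervals.
2. Fix any non-linear term in advance, rather than adding it if the linear fit looks poor.
3. Keep impaired versus normal TAPSE as a secondary summary and for the Kaplan-Meier display, with its cut-off stated.
4. Label 1.62/0.46 at 80% power as the detectable effect of the unadjusted dichotomised comparison only. Say that the chi-squared test is a power approximation, if that is what was meant.

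The cost is wording: Table 2 already lists SAPS-II, TAPSE, RV s' and 90-day mortality as collected. The small downside is that a straight-line term has less power than the cut if risk changes sharply at the cut. The secondary comparison, and a non-linear term if one is fixed in advance, are there for that case.

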4.6. Runtime

Since 10 February 2016.

4.7. Primary analysis

The association between RV-function measured by TAPSE or RV s' and 90-day mortality.

4.8. Secondary analysis

The association between RV-function measured by TAPSE or RV s' and clinical examination findings and cardiac output.

5. Abdominal flow

5.1. Research question

Is peripheral blood flow measured with CCUS associated with cardiac output?

5.2. Variables of interest

Common carotid artery, subclavian artery, and common femoral artery flows have been measured with the linear probe 8L or 9L and default carotid setting of the General Electric Vivid-S6 mobile ultrasound machine. A proxy for abdominal flow was calculated by subtracting flow over both left and right carotid, subclavian and femoral arteries from the cardiac output.

5.3. Timing of measurement

During inclusion in the basic study (one-time snapshot).

5.4. Additional exclusion criteria

Obstruction of the desired window of peripheral artery flow (e.g. by a central venous or dialysis catheter, postsurgical incisions, wounds, etc.).

5.5. Sample size, power and detectable difference

We will conduct analyses of this sub-study with 59 patients, in which we will regress their values of cardiac output against peripheral flow measurements such as common carotid artery flow. Our pilot data indicate that the standard deviation of common carotid artery flow is 7.9, with an estimated standard deviation of the regression errors of 97. If the true slope of the line obtained by regressing cardiac output against common carotid artery flow is 5.4, we will be able to reject the null hypothesis that this slope equals zero with probability (power) 80%. The type I error probability associated with this test of this null hypothesis is 0.015.

5.6. Runtime

14 April 2016 until 17 August 2016.

5.7. Primary analysis

The association between peripheral blood flow measured at the common carotid, subclavian, and common femoral arteries and cardiac output.

5.8. Secondary analysis

The association between a proxy for abdominal organ blood flow and acute kidney injury (AKI) or 90-day mortality.

6. FloTrac

6.1. Research question

What is the level of agreement between cardiac output measured by the FloTrac compared to cardiac output measured with CCUS?

6.2. Variable of interest

Cardiac output has been estimated with the FloTrac (Edwards Lifesciences, Irvine, California, USA) and a monitor to compute stroke volume and cardiac output (Vigileo, Edwards Lifesciences, Irvine, California, USA). The FloTrac analyses the arterial pressure waveform to compute stroke volume and cardiac output. The estimated cardiac output was compared to the cardiac output measured with the General Electric Vivid-S6 mobile ultrasound machine.

6.3. Timing of measurement

Paired cardiac output measurements were conducted after admission every hour for 4 hours and once 24 hours after admission.

6.4. Additional exclusion criteria

Patients not requiring vasopressors and/or inotropes, an inadequate acoustic window for cardiac output measured by CCUS, absence of an arterial line, atrial fibrillation during inclusion, aortic and/or mitral valve disease.

6.5. Sample size, power and detectable difference

We are planning a study with paired measurements in 55 patients. Prior pilot data indicate that the difference in the cardiac output of both measurements devices is normally distributed with standard deviation 0.86. If the true difference in the cardiac output of both measurements devices is 0.39, we will be able to reject the null hypothesis that this response difference is zero with probability (power) 80%. The type I error probability associated with this test of this null hypothesis is 0.015.

6.6. Runtime

Since June 1st, 2016.

6.7. Primary analysis

The level of agreement between cardiac output measured by the FloTrac and cardiac output measured with CCUS.

6.8. Secondary analysis

The changes in levels of agreement when factors that might influence FloTrac measurements are present.

7. Repeated measurements

7.1. Research question

Are changes in clinical examination findings over 24 hours associated with changes in cardiac output?

7.2. Variable of interest

We repeated the measurements of the variables collected in the basic study, sub-study 2, and sub-study 4. We performed these measurements 24 hours (minimum 22 to maximum 26 hours) after the first measurement and calculated differences. The sign of the variable indicates whether a variable has either increased (positive number) or decreased (negative number).

7.3. Timing of measurement

During inclusion in basic study and 24 hours (minimum 22 hours to maximum 26 hours) thereafter.

7.4. Additional exclusion criteria

Patients not requiring vasopressors and/or inotropes, expected stay less than 48 hours.

7.5. Sample size, power and detectable difference

We are planning to conduct this sub-study with 100 patients and we will regress their values of difference in cardiac output changes over 24 hours against clinical examination findings such as central-to-toe temperature difference. Prior data indicate that the standard deviation of central-to-toe temperature is 4.1 with an estimated standard deviation of the regression errors of 1.35. If the true slope of the line obtained by regressing changes in cardiac output against central-to-toe temperature differences is 0.16, we will be able to reject the null hypothesis that this slope equals zero with probability (power) 80%. The type I error probability associated with this test of this null hypothesis is 0.015.

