7.7. Primary analysis

The association between changes in clinical examination findings over 24 hours and changes in cardiac output.

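### Sub-study 7: the slope of 0.16 at 80% power does not follow from the printed inputs, and the predictor SD of 4.1 is labelled as a level although the planned predictor is a 24-hour change

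*SAP*

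**What the plan says.** Section 7.5 of SAP Appendix 1 fixes the size of the sub-study: "We are planning to conduct this sub-study with 100 patients". It names central-to-toe temperature difference as an example predictor and gives two standard deviations: "Prior data indicate that the standard deviation of central-to-toe temperature is 4.1 with an estimated standard deviation of the regression errors of 1.35". The detectable effect is the slope obtained by "regressing changes in cardiac output against central-to-toe temperature differences is 0.16", for which the section claims "we will be able to reject the null hypothesis that this slope equals zero with probability (power) 80" per cent. It adds: "The type I error probability associated with this test of this null hypothesis is 0.015".

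Other parts of the same sub-study define the predictor as a change. Section 7.2 repeats the measurements about 24 hours after the first, calculates differences, and explains their direction: "The sign of the variable indicates whether a variable has either increased (positive number) or decreased (negative number"). Section 7.7 gives the primary analysis as: "The association between changes in clinical examination findings over 24 hours and changes in cardiac output".

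The value 4.1 also stands in section 1.5, for the NIRS sub-study: "Prior data indicate that the standard deviation of central-to-toe temperature is 4.1 with and estimated standard deviation of the regression errors of 23". Section 1.3 describes that sub-study's measurement as a one-time snapshot.

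**The concern.** There are two faults in one sentence of section 7.5, and both bear on the same number.

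- **Arithmetic.** A detectable slope is fixed by the sample size, the predictor SD, the residual SD, the type I error and the power. All five are printed, and they do not agree with the printed slope.
- **Predictor.** Power for a slope depends on the spread of the variable that enters the regression. Here that is a within-patient change over 24 hours. The printed SD carries the label of a level, and its value and near-identical wording recur in a sub-study with one measurement per patient. The SAP gives no SD identified as that of the change.

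Section 7.5 is the SAP's only statement of what sub-study 7 can detect, so a null result would be read against it. As printed, the reader cannot tell whether the planned regression is more or less sensitive than stated.

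**Working it through.** **Inputs (section 7.5).** N = 100; predictor SD, SDx = 4.1; residual SD, s = 1.35; slope b = 0.16; power 0.80; type I error 0.015. The section does not state sidedness, so two-sided is assumed.

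**Formula.** For the slope test in simple linear regression, the noncentrality is b × SDx × √N / s. It is referred to a noncentral t distribution with N − 2 degrees of freedom.

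**Step 1: does this formula match the SAP's other slope calculations?**
- Section 1.5 (N = 32, SDx = 4.1, s = 23, b = 3.406): noncentrality 3.406 × 4.1 × √32 / 23 = 3.43, power 0.797. The SAP states 80%.
- Section 5.5 (N = 59, SDx = 7.9, s = 97, b = 5.4): noncentrality 5.4 × 7.9 × √59 / 97 = 3.38, power 0.804. The SAP states 80%.

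Both are reproduced, so the method and the two-sided reading fit the SAP's practice.

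**Step 2: section 7.5 with its own inputs.**
- Noncentrality 0.16 × 4.1 × √100 / 1.35 = 6.56 / 1.35 = 4.86. The critical t on 98 degrees of freedom is 2.476. Power is 0.991, not 0.80.
- Slope detectable at 80% power: 0.109. Normal approximation: (2.432 + 0.842) × 1.35 / (4.1 × 10) = 0.108.
- A one-sided test gives 0.100. Reading 1.35 as the SD of the outcome instead of the errors raises power at 0.16 to 0.999. Neither rescues 0.16.
- With the other inputs as printed, 0.16 at 80% power would need one of the following: SDx of about 2.80, s of about 1.97, or N of about 49.

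**Step 3: what the planned predictor implies.** The SAP gives no SD for the 24-hour change, so only an illustration is possible. Assumptions: SD of 4.1 at both time points, within-patient correlation rho, and s held at 1.35. Then the SD of the change is 4.1 × √(2(1 − rho)).

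| rho (assumed) | SD of change | Slope at 80% power | Power at 0.16 |
|---|---|---|---|
| 0.3 | 4.85 | 0.093 | >0.99 |
| 0.5 | 4.10 | 0.109 | 0.99 |
| 0.6 | 3.67 | 0.122 | 0.97 |
| 0.7 | 3.18 | 0.141 | 0.90 |
| 0.8 | 2.59 | 0.173 | 0.72 |
| 0.9 | 1.83 | 0.245 | 0.385 |

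The SD of the change equals 4.1 only at rho = 0.5. The SD of 2.80 that makes the printed pair true corresponds to rho = 1 − (2.80/4.1)²/2, about 0.77.

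**The case against.** The strongest reply is that 0.16 may be the right figure for the change regression and only the printed SD is wrong. An SD of change of about 2.8 is well within what one could expect, and it gives exactly 80% power at 0.16. That stands. The documents do not show that 0.16 is wrong for the planned analysis; they show that 0.16 and 4.1 cannot both be right with the other inputs.

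For the same reason, a reader might infer that the SAP derived 0.16 by putting the level SD of 4.1 into the formula. It did not, at least not with the other printed inputs, because those give 0.109. A reader might also infer that the sub-study is underpowered, or that power is overstated by a known amount. That is not supported either. The benchmark is the stated 80%, and below a correlation of about 0.77 the stated figure is conservative.

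The wording is also open. Central-to-toe temperature difference can mean the core-to-toe gradient or its change over time, and section 7.5 attributes 4.1 only to prior data. That it is a level SD from another group is an inference from the match with section 1.5. If 4.1 were in fact the SD of the change, the predictor point would fall, but the arithmetic mismatch would remain.

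Finally, the stakes are low. SAP section 2.2.3 makes the basic study the scope of the plan and leaves the sub-study SAPs for later. The introduction to Appendix 1 calls the sub-study conclusions explorative, to be confirmed in separate cohorts. Temperature is only an example predictor. This limits the severity but does not make the sentence correct.

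**Conclusion.** The point holds as a minor error. The printed inputs of section 7.5 give about 99% power at a slope of 0.16, or a slope of about 0.109 at 80% power. This rests only on the printed figures and a two-sided test, and the same formula reproduces sections 1.5 and 5.5.

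The second part is a mismatch of label and predictor: the SD given is that of a level on its most natural reading, and the regression uses a change. Correcting the arithmetic at 4.1 would therefore not settle the matter unless the SD of the change happens to be 4.1.

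The direction of the error is unknown. With residual SD 1.35, power at 0.16 exceeds 80% if the SD of the change is above about 2.8 and falls short if it is below.

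**What to change.** In Appendix 1, section 7.5:

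1. State the SD of the 24-hour change in central-to-toe temperature, labelled as such. SAP Table 2 lists the central-to-peripheral difference at baseline and after 24 hours for this sub-study, so the SD can be obtained without examining its association with cardiac output.
2. Name the source of the residual SD. It should come from prior or pilot data and not from fitting the sub-study 7 primary regression.
3. Restate the detectable slope, or the power at 0.16, at N = 100 and type I error 0.015, so that it follows from the printed inputs. State that the test is two-sided, if it is.
4. If a range is given until the SD is known, label it as an assumption: equal SDs of 4.1 at both times, residual SD 1.35, and a stated span of correlations.

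The cost is one SD from variables already scheduled for collection and one revised sentence, with no extra patients. The drawback is that the stated sensitivity may become less favourable.
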